3 OBJECTIVES AND ENDPOINTS

TABLE 2: OBJECTIVES & ENDPOINTS

OBJECTIVES	ENDPOINTS	JUSTIFICATION FOR ENDPOINTS
Primary		
To determine whether TTFIELDS combined with adjuvant temozolomide increases OS in patients with newly diagnosed Grade II and III astrocytoma with TERT promoter mutation only compared to historical and contemporaneous controls.	OS measured in days from Study Day 0 until death. If the study ends and the participant is still living, OS will be measured in days from Study Day 0.	OS remains the primary concern within this patient population. Intent to Treat analysis will be used to determine if this objective is met.
Secondary		

 To determine whether the combination of TTFIELDS and adjuvant temozolomide is safe in the newly diagnosed high-risk Grade II and III astrocytoma. To determine whether TTFIELDS combined with adjuvant temozolomide increases PFS in patients with newly diagnosed Grade II and III astrocytoma with TERT promoter mutation only compared to historical and contemporaneous controls. To evaluate QOL using KPS, EORTC QLQ-C30/BN20, and MMSE in patients treated with TTFIELDS combined with adjuvant temozolomide compared to 	
 PFS measured in days from Day 0 to progression Safety measured by incidence and severity of Adverse Events and Toxicities. Quality of life measured by KPS, EORTC QLQ-C30/BN20, and MMSE Correlation between % Compliance with TTFIELDS and OS 	Safety, Efficacy, and Quality of Life measures for a more complete view of the effects of the study treatment(s).

historical and contemporaneous controls.		
Tertiary/Exploratory		

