5.5 Strategies for Recruitment and Retention

Potentially eligible patients scheduled to undergo maximal surgical resection of a Grade II or III astrocytoma will be identified through direct referral at participant sites. PHI will be reviewed by the PI(s) and/or Study Coordinator but not recorded in order to pre-screen patients for eligibility for this trial. The pre-screening PHI will consist of a review of the medical records to confirm new diagnosis in adults age 18 years or older, as well as tumor cytogenetic and DNA sequencing characteristics (Mutational identity determined by CLIA-certified sequencing as possessing a IDH1/2 wildtype and TERT promoter mutated genotype).

Since high-risk astrocytomas are only approximately 10% of all Grade II and III gliomas, only those patients who have appropriate tumor characteristics after biopsy will be approached about the study. Potential subjects will be approached well in advance of study commencement to ensure sufficient time for review of the informed consent form and other logistical coordination.

Since the primary outcome of the study is overall survival, each patient's Legally Authorized Representative (LAR) will be recorded at enrollment. In the event that the subject loses capacity to consent for himself/herself during the course of the study, the LAR will be approached for the Survival Follow-up items (only) for that subject.

Information on this study will be posted on ClinicalTrials.gov. Recruitment is planned for 36 months in total.

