6.3 Correlative Studies

6.3.1 Tumor Tissue Specimens

6.3.1.1 Collection of specimens

Formalin fixed and paraffin embedded (FFPE) samples will be obtained from pathology or research tissue banks from primary tumors and first recurrent tumors, when available. One FFPE tissue block or fifteen slides of 20 µm thick section will be required for analysis. At least 20 pairs of primary tumors and first recurrent tumors from patients treated only with RT and concurrent temozolomide followed by adjuvant temozolomide, and not with TTFields or any other modalities (drug, radiation or device), are needed.

The Coordinating Center will obtain at least 20 historical paired samples from patients with the same tumor type or GBM before and after being treated with temozolomide and RT, but not with TTFields, over the last 5 years at the same participating institutions.

Sequencing analyses will be obtained by standard of care sequencing (immunohistochemistry or next-generation sequencing), from which mutation burden data will be obtained. Mutation burden will be expressed as number of mutations per Mb and will be extracted from sequencing reports for primary tumors and first recurrent tumors, where available.

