9.2 Control Cohort Inclusion Criteria

In order to be eligible to enroll in the control cohort, an individual must meet all of the following criteria:

- A. Willing and able to provide written informed consent or eligible for inclusion under an IRB-approved waiver of consent
- B. Male or female, 18 years or older

- C. Histologic confirmation of WHO Grade II or III astrocytoma
 - a. mixed oligoastrocytomas are permitted
- D. Mutational identity determined by CLIA-certified sequencing including:
 - a. IDH1/2 wildtype (i.e. lack of detectable mutations on the sequencing report, variants of unknown significance or non-synonymous single nucleotide polymorphisms deviating from wild-type sequence do not apply)
- AND
- b. TERT promoter mutation(s)
- E. Karnofsky performance status $\geq 70\%$
- F. Maximal safe resection
 - a. biopsy alone is allowed
- G. Completed standard chemoradiation and concurrent temozolomide and adjuvant temozolomide.
 - a. Patients with a tumor that was biopsied or resected in the past followed by observation only without definitive chemoradiation and/or chemotherapy given will be eligible, as long as: repeat maximal surgical resection (biopsy only allowed) has been performed, definitive temozolomide/RT treatment meets the criteria above, and adjuvant temozolomide treatment was given (or planned for the contemporaneous cohort)
- H. Candidate for adjuvant high dose temozolomide per investigator's clinical judgement (for the contemporaneous cohort)
- I. No evidence of early disease progression per RANO criteria upon completion of Chemo/RT and beginning adjuvant temozolomide

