9.3 Control Cohort Exclusion Criteria

At time of starting adjuvant (first-line) therapy:

- L. Prior treatment with anti-angiogenic agents including bevacizumab.
- M. Progressive disease (according to RANO criteria) after temozolomide/RT, at time of starting adjuvant therapy.
- N. Actively participating in another clinical treatment trial intended to treat the underlying astrocytoma at start of adjuvant Temozolomide treatment.

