10.2 Sample Size Determination

To assess sample size requirements for detecting an improvement in median overall survival (OS) in the experimental treatment arm relative to the historical control arm, we initially assumed 60 to 90 patients receiving standard treatment and follow-up between 1-2016 and 5-2019 would be available for chart review. We assumed that these historical control patients would have a maximum follow-up time of 60 months. For the experimental treatment, we assumed an accrual rate of 2.5 patients per month across 15 participating centers and an accrual period of 36 months, yielding an enrollment of 90 patients in the experimental arm. The patients in the experimental arm would be followed for an additional 24 months after the end of accrual. We considered improvements in median survival ranging from 4 to 8 months to be of clinical interest. We also assumed that survival times would follow a Weibull distribution with proportional hazards and an accelerating hazard function (shape parameter $k=2.0$, estimated from Figure 3A in Eckel-Passow et al [12]. We also considered a more slowly accelerating Weibull shape parameter of $k=1.8$. Under these assumptions, the power to detect **improvements** in median OS using a one-sided log-rank test (one-sided $\alpha=0.05$) are summarized in Table 10 for selected combinations of historical control sample size, Weibull shape parameter, and number of months improvement in median OS [detectable effect size methodology adapted from (Wu and Xiong, 2014)]. We then explored the effect of mixing historical and contemporaneous controls in select mixtures into a single control arm, noting a very slight improvement in power to detect improvements in survival. Overall, a control arm sample size of 90 patients, in historical/contemporaneous control mixtures of 90+0, 80+10, 70+20, and 60+30 all have at least 80% power to detect improvements in survival between 6 and 8 months.

TABLE 10: POWER TO DETECT M MONTHS IMPROVEMENT IN MEDIAN OVERALL SURVIVAL UNDER SELECTED SCENARIOS

Accrual rate (N/mo)	Accrual period (mos)	Follow-up period (mos)	Trial N	Hx Ctl+ Contemp N	Weibull shape k	Power to detect M months improvement in median OS at one-sided $\alpha=0.05$ using the log-rank test				
						M = 4	5	6	7	8
2.5	36	24	90	50+ 0	2.0	0.525	0.667	0.782	0.866	0.922
2.5	36	24	90	60+ 0	2.0	0.565	0.711	0.823	0.899	0.946
2.5	36	24	90	70+ 0	2.0	0.598	0.745	0.853	0.922	0.962
2.5	36	24	90	80+ 0	2.0	0.626	0.773	0.876	0.938	0.972

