10.2.1 Analysis of Primary and Secondary Endpoints and Correlative Studies

We will compare OS and progression-free survival (PFS) between historical control and experimental treatment arms using the log-rank test (we will also collect PFS data via chart review for the historical control patients). For our correlative studies, we will use the independent-sample t test to compare mean mutation burden between patient samples treated with RT+temozolomide or RT+temozolomide+TTFields. We may perform the same comparison within a linear regression framework if the need arises to adjust for any potential confounders for the effect of TTFields in our correlative studies.

To investigate the influence of electric field and energy deposition in the tumor on outcomes, we will use the Wilcoxon rank sum test to compare the electric field and specific absorption ratio parameters between: responders and non-responders; subjects with progression-free survival \geq and $<$ 1 year; subjects with overall survival \geq and $<$ 2 years; and subjects with overall survival \geq and $<$ 1.5 years. We will estimate Pearson correlation coefficients to assess the correlation of OS and PFS with electric field or specific absorption ratio parameters.

We may stratify the patients by MGMT methylation status, extent of resection, or a combination of the two.

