11.2.2.1 Control Cohort Enrollment Documentation Requirements

The following documentation is required for control subject enrollment. All documents should be uploaded into the eCRF within 45 days of enrollment.

1. Signed and dated Informed Consent Form
2. Documentation of consent checklist
3. Pathology Report including MGMT methylation status. If not feasible or indeterminate, must be stated. Indeterminate methylation status will be considered unmethylated.
4. Immunohistochemistry or next-generation sequencing Report (e.g. Foundation Medicine, TEMPUS, Caris, or similar CLIA-certified sequencing service)
5. Screening MRI Report; RANO forms are not required at time of enrollment.
6. Signed and dated enrollment checklist

Additionally, the following data shall be entered into the eCRF at enrollment and source documentation included:

- a. KPS
- b. Resection Summary
- c. Chemo/Radiation Summary

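### The control genotype criterion sets no date or specimen limit, so a historical control who qualifies only through testing at recurrence or later is counted from Day 0 despite having had to survive to the test; if untested patients die earlier, this costs power against TTFields

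*Combined protocol and SAP*

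**What the plan says.** For controls, section 9.2 D asks for "Mutational identity determined by CLIA-certified sequencing including" IDH1/2 wildtype and TERT promoter mutation. It gives no date and names no specimen. Item 4 of section 11.2.2.1 requires "Immunohistochemistry or next-generation sequencing Report (e.g. Foundation Medicine, TEMPUS, Caris, or similar CLIA-certified sequencing service") and sets no limit on its date. The data list in section 9.5 has operation, temozolomide, progression and death dates, but no sequencing date. The control exclusions in section 9.3 do have a time anchor, "At time of starting adjuvant (first-line) therapy", but it governs only the exclusions. Sections 10.1 and 10.3 say that historical controls would have met first-tier criteria, a term that is not defined and sets no sequencing date.

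For device patients, section 5.5 says "only those patients who have appropriate tumor characteristics after biopsy will be approached about the study". Their genotype is therefore known before consent.

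Section 6.3.1.1, on the mutation-burden study, says the data "will be extracted from sequencing reports for primary tumors and first recurrent tumors, where available". Reports on recurrent tumours are thus expected to exist.

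Table 2 in section 3 has "OS measured in days from Study Day 0 until death". Section 10.2.1 compares OS and progression-free survival (PFS) "between historical control and experimental treatment arms using the log-rank test", with no landmark or late-entry rule.

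**The concern.** Historical controls are found by chart review among patients who completed chemoradiation between 1 January 2016 and 20 May 2019. Suppose a patient's primary tumour was never sequenced and the qualifying report was ordered at recurrence. That patient is in the cohort only because he or she lived long enough to be tested. A similar patient who died first has no report and cannot be included. Counting the included patient at risk from Day 0 adds survival time that was guaranteed by the way the patient was found.

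The device arm has no counterpart, because its genotype precedes Day 0. At stake is an understated device effect and a possible false negative on the primary endpoint, in a plan whose own power at shape 1.8 (0.820 for a 6-month gain) is barely above its stated 80%.

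**Working it through.** **1. The plan's own figure.** Inputs from sections 10.1 and 10.2: control median 22 months, gain M = 6, 90 v 90, accrual 36 months plus 24 months of follow-up (24-60 months per patient), one-sided α = 0.05.

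HR = (22/28)^k, which is 0.617 at k = 2.0 and 0.648 at k = 1.8. At k = 2.0, with both arms followed 24-60 months, expected deaths are 78.4 (control) and 67.6 (device), 146.0 in all.

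Power = Φ(|ln HR|·√(146.0 × 0.25) − 1.645) = Φ(0.4823 × 6.041 − 1.645) = Φ(1.27) = 0.898. Table 10 has 0.894. At k = 1.8 the result is 0.827 against 0.820. Over 45 cells checked, the largest gap is 0.8 points, so Table 10 reproduces.

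**2. Effect on the control curve.** Let a share f of controls be included only if alive at time τ. For t > τ the control curve becomes S(t)·[(1 − f) + f/S(τ)]. Both f and τ are assumptions.

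At k = 2.0, f = 20%, τ = 12 months: S(12) = exp(−0.693 × (12/22)²) = 0.814. The factor is 0.8 + 0.2/0.814 = 1.046. The median solves S(t) = 0.5/1.046 = 0.478, so t = 22 × √(0.738/0.693) = 22.7 months. The same sum gives 22.2 months at τ = 6 and 23.7 at τ = 18.

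**3. Effect on power.** Simulated log-rank test, M = 6, late-tested controls alive at a time uniform on 3-18 months, 10,000 trials per cell. Device patients are followed 24-60 months; controls 24-60 or a full 60 months.

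| Share tested late | k=1.8, 24-60 | k=1.8, 60 | k=2.0, 24-60 | k=2.0, 60 |
|---|---|---|---|---|
| 0% | 0.82 | 0.85 | 0.90 | 0.91 |
| 10% | 0.78 | 0.81 | 0.88 | 0.90 |
| 20% | 0.75 | 0.78 | 0.84 | 0.88 |
| 30% | 0.70 | 0.74 | 0.82 | 0.84 |
| 40% | 0.66 | 0.70 | 0.79 | 0.82 |

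Shorter runs put the 10-40% range at 0.79 to 0.64 for k = 1.8 and 0.88 to 0.82 for k = 2.0. The follow-up assumption and simulation error (about 0.01 with 2,000 trials) explain the differences. With no device effect, the expected HR at k = 1.8 rises from 1.00 to about 1.02-1.11, and one-sided type I error falls below 0.05.

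**4. Testing tied to recurrence.** Step 3 imposes the survival advantage by drawing late-tested controls as random survivors. A recurrence model tests whether it arises. Assumed: median PFS 8 or 11 months, median OS 22 months, report 1.5 months after recurrence, a share q dying without a testable recurrence, 20% or 40% of controls tested at recurrence, no device effect, 1,500 trials per setting.

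| q | Type I error, counted from Day 0 | Type I error, delayed entry at report |
|---|---|---|
| 0% | 0.03-0.05 | 0.10-0.34 |
| 10% | 0.02-0.03 | 0.07-0.28 |
| 25% | 0.01-0.03 | 0.06-0.17 |

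With q = 0, counting from Day 0 does almost no harm; the conservative bias grows with q. In a related model (median PFS 7-14 months, q 5-25%), patients sequenced at recurrence had median OS of 22.5-28.9 months against 22 overall, so the direction holds whenever some patients die untested.

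**5. Delayed entry.** The right-hand column shows why entry at the report date is not a safe correction. A patient tested because of recurrence enters the risk set just as the hazard rises. Control survival then looks too short and the error favours TTFields.

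**The case against.** - **No document shows that any control was first tested late.** This stands. The sentence on recurrent-tumour reports in section 6.3.1.1 belongs to the correlative study. It shows that such reports exist, not that one is ever a control's only report. The share and the delay are assumptions.
- **Not all 90 controls are exposed.** This stands. The 10-30 contemporaneous controls qualify for the trial and decline the device, so they are normally genotyped before Day 0. The issue mainly concerns the 60-80 historical controls. A share of 40% of 90 is 36 patients: 45% of 80 or 60% of 60, which is a high figure.
- **Power mostly survives at the plan's main shape.** Largely true. At k = 2.0 it drops below 0.80 only at the extreme of the range.
- **Late testing could be traced anyway.** This stands in part. A reader might infer that the problem cannot be seen afterwards. In fact section 11.2.2.1 has the reports uploaded and section 11.1.7 makes REDCap the source repository, so late reports could be found. What is missing is a date field and an analysis rule.
- **The bias is conservative.** This stands. A reader might infer that the primary result could be falsely positive. Guaranteed survival in the control arm works the other way.

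Two groups are unaffected: patients under 9.2 G.a sequenced at the repeat surgery before chemoradiation, and patients whose archived primary tissue was tested regardless of outcome.

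**Conclusion.** The gap is real: the genotype criterion has no time anchor for controls, the device arm is genotyped before Day 0, and the analysis counts everyone from Day 0. Control inclusion can therefore depend on survival. If untested patients die earlier, the consequence is lost power and an understated effect, not a false positive.

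The size cannot be read from the documents. It ranges from near zero, if nearly all patients reach recurrence and can be tested, to the losses in step 3. At k = 1.8 a share of 20% already takes power for a 6-month gain below the stated 80%; at k = 2.0 it does not.

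These figures take Day 0 for controls as the start of adjuvant temozolomide, since the plan gives controls no Day 0 of their own. The point merits a change because the change is cheap, not because a large bias has been shown.

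**What to change.** 1. Amend 9.2 D so that the qualifying report predates the start of adjuvant temozolomide, or comes from tissue removed before that date and tested regardless of clinical course.
2. Add specimen date and report date to the control eCRF and to section 9.5.
3. If later-tested controls are kept to reach 90, prespecify a sensitivity analysis of OS and PFS that excludes them.
4. Do not use delayed entry at the report date as the correction.

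The cost is two chart dates per control, one clause and one analysis. No patient's treatment changes.

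The downside is that some controls may be lost, and section 9 requires at least 90. Table 10 prices this at M = 6 with 70 instead of 90 controls: 0.853 against 0.894 at k = 2.0, and 0.771 against 0.820 at k = 1.8. Exclusion therefore need not raise power. What it buys is a control arm whose membership does not depend on survival. Replacing excluded controls, where the sites can, avoids the loss.

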5 STUDY POPULATION

5.1 Inclusion Criteria

In order to be eligible to participate in this study, an individual must meet all of the following criteria:

- A. Willing and able to provide written informed consent
- B. Stated willingness to comply with all study procedures and availability for the duration of the study
- C. Male or female, 18 years or older
- D. Life expectancy of at least 3 months
- E. Histologic confirmation of WHO Grade II or III astrocytoma
 - a. mixed oligoastrocytomas are permitted
- F. Mutational identity determined by CLIA-certified sequencing including:
 - a. IDH1/2 wildtype (i.e. lack of detectable mutations on the sequencing report, variants of unknown significance or non-synonymous single nucleotide polymorphisms deviating from wild-type sequence do not apply)
AND
 - b. TERT promoter mutation(s)
- G. Karnofsky performance status $\geq 70\%$
- H. Maximal safe resection
 - a. biopsy alone is allowed
- I. Completed standard chemoradiation with total RT dose of at least 40 Gy and concurrent temozolomide (75mg/m² daily dose with 80% prescribed dose completed)
 - a. Patients with a tumor that was biopsied or resected in the past followed by observation only without definitive chemoradiation and/or chemotherapy given will be eligible, as long as: repeat maximal surgical resection (biopsy only allowed) has been performed, definitive temozolomide/RT treatment meets the criteria above, and adjuvant temozolomide treatment is planned
- J. Candidate for adjuvant high dose temozolomide per investigator's clinical judgement
- K. Adjuvant Temozolomide start date at least 4 weeks, but not more than 6 weeks, from the later of last dose of concomitant temozolomide or radiotherapy
- L. No evidence of early disease progression per RANO criteria at the time of enrollment
- M. Women of childbearing potential (WOCBP) must be using a highly effective method of contraception to

avoid pregnancy throughout the study and for at least 24 weeks after the last dose of study drug to minimize the risk of pregnancy.

- a. Prior to study enrollment, women of childbearing potential must be advised of the importance of avoiding pregnancy during trial participation and the potential risk factors for an unintentional pregnancy.
 - b. Refer to section 10.2.1 for guidance on highly effective contraceptive methods acceptable in this study.

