9 CONTROL COHORT

This trial will include a control cohort that includes both historical and contemporaneous control patients. A minimum of 90 and a maximum of 100 patients will be enrolled in the control cohort. This is a non-interventional control group (data collection only). All patients in the control cohort will be enrolled at the same participating institutions. Risks associated with participation of the control cohort are minimal.

Historical controls will be gathered via chart review of patients completing chemo/RT after 1/1/2016 and before 5/20/2019; 5/20/2019 is the initial date of IRB approval for the coordinating center and first opened study site. Control patients completing chemo/RT after 5/20/2019 will be enrolled as contemporaneous controls.

Control subjects (contemporaneous or historical) will be enrolled via informed consent if consent is practicable. An IRB waiver of consent will be requested for historical control patients who may be deceased, no longer being followed or lost to follow-up.

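### Control criterion 9.2 G, as worded, requires completed adjuvant temozolomide, while most of the plan judges control eligibility at its start; the wording should be reconciled

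*Combined protocol and SAP*

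**What the plan says.** Section 9.2 requires a control to meet every listed criterion. Criterion G reads "Completed standard chemoradiation and concurrent temozolomide and adjuvant temozolomide": one verb, with adjuvant temozolomide among its objects.

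The surrounding text is looser:

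- G.a, for patients observed after an earlier biopsy or resection, asks that "adjuvant temozolomide treatment was given (or planned for the contemporaneous cohort").
- H asks contemporaneous controls only to be candidates for adjuvant temozolomide.
- I requires "No evidence of early disease progression per RANO criteria upon completion of Chemo/RT and beginning adjuvant temozolomide".
- The exclusions in 9.3 open with "At time of starting adjuvant (first-line) therapy".
- Section 9 dates the cohort by chemoradiation: "Historical controls will be gathered via chart review of patients completing chemo/RT after 1/1/2016 and before 5/20/2019".
- Sections 10.1 and 10.3 say that historical controls would have satisfied the trial's first-tier entry criteria (a term not defined).
- Section 11.2.2.1 lists the control enrolment documents. None is proof that adjuvant treatment was completed.

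For the interventional arm, 5.1 I stops at chemoradiation: "Completed standard chemoradiation with total RT dose of at least 40 Gy and concurrent temozolomide". Criteria J and K add candidacy and a start window for adjuvant temozolomide, but no completion.

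Table 2 counts OS from Study Day 0, which 8.1.1 identifies as the start of temozolomide cycle 1. Section 6.1.1.3.1.9 starts PFS at cycle 1 day 1. Neither origin is stated separately for controls. Section 10.2.1 compares the arms with a log-rank test and mentions no delayed entry or landmark.

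**The concern.** Completing adjuvant temozolomide happens months after Day 0. A chart reviewer who applies G as written drops every historical patient who died before finishing, while trial patients who die in the same window are counted. The retained controls then carry survival time in which death was impossible, and their survival curve is shifted upward.

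Historical patients are expected to be 60 to 80 of the 90 controls (10.1), so this touches most of the comparator for the primary endpoint. An analysis cannot restore patients who were never abstracted. The trial plans 10 to 20 centers, and each could read G differently, so the control arm could depend on the reader.

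**Working it through.** **Inputs from the plan (10.1, 10.2).** Control median 22 months; Weibull shape k=2.0, alternative 1.8; 90 TTFields patients accrued over 36 months and followed 24 more; 90 controls in mixes from 80+10 to 60+30 (historical + contemporaneous); one-sided log-rank at 0.05; gain in median OS of M months.

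**Assumptions.** Controls are taken to complete 6 or 12 cycles of 28 days. That is the interventional range in 6.1.1.1; none is given for controls. Censoring is uniform over 24-60 months for TTFields and contemporaneous patients, and over 20-60 months for historical controls. Only historical controls are conditioned on survival.

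**Reproducing Table 10.** HR = (22/(22+M))^k. For M=6, k=2: (22/28)^2 = 0.617. With 24-60 months of follow-up in both arms, expected deaths are 78.4 + 67.6 = 146.0. Schoenfeld: sqrt(146.0 × 0.25) × |ln 0.617| − 1.645 ≈ 1.27, so power is 0.898, against 0.894 stated for 90+0. The simulation used below (60,000 runs per cell), with no conditioning and an 80+10 mix, gives 0.886 at k=2 (stated 0.894) and 0.816 at k=1.8 (stated 0.821).

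**Time that completion guarantees.** Last dose of cycle 6 is day 5×28+5 = 145, and the cycle ends on day 168. Last dose of cycle 12 is day 11×28+5 = 313, and the cycle ends on day 336. Dividing by 30.44 gives 4.76, 5.52, 10.28 and 11.04 months.

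**Share dead by then:** q = 1 − exp(−ln 2 × (t/22)^k). **Power at M=6** with historical controls conditioned on being alive at t:

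| Alive at | t (months) | q, k=2 | q, k=1.8 | k=2, 80+10 | k=2, 60+30 | k=1.8, 80+10 | k=1.8, 60+30 |
|---|---|---|---|---|---|---|---|
| Last dose, cycle 6 | 4.76 | 0.032 | 0.043 | 0.851 | 0.863 | 0.741 | 0.763 |
| End of cycle 6 | 5.52 | 0.043 | 0.056 | 0.838 | 0.853 | 0.719 | 0.745 |
| Last dose, cycle 12 | 10.28 | 0.141 | 0.162 | 0.656 | 0.730 | 0.469 | 0.569 |
| End of cycle 12 | 11.04 | 0.160 | 0.182 | 0.610 | 0.697 | 0.416 | 0.530 |

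**Larger gains.** At 6 cycles, M=7 gives 0.92-0.93 (k=2) and 0.82-0.86 (k=1.8), and M=8 gives 0.90 or more at both shapes. At 12 cycles, M=7 gives 0.75-0.85 and 0.57-0.71; M=8 gives 0.86-0.92 and 0.69-0.81.

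**Control median.** The conditioned median is 22 × (1 + (t/22)^k)^(1/k). At the last dose of cycle 6 and of cycle 12 this is 22.5 and 24.3 months (k=2), or 22.8 and 25.0 months (k=1.8).

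**Type I error (M=0).** It falls from 0.05 to 0.022-0.037 (6 cycles) or 0.002-0.010 (12 cycles).

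**Estimated effect (M=6, k=2).** The true HR of 0.617 appears as 0.63-0.64 (6 cycles) or 0.68-0.72 (12 cycles).

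**The case against.** The strongest reply is that completion cannot have been intended. It would make H empty, since a candidate for adjuvant treatment has not finished it. It would hold ordinary controls to a stricter standard than the G.a subgroup for no stated reason. It gives sites no threshold, because no cycle number is set for controls; 9.5 item 7 records cycles as data. It conflicts with the tie to the trial's own entry criteria in 10.1 and 10.3, and the enrolment documents would not verify it. The bias is also conservative, and at 6 cycles with the plan's main shape the 80% power claim survives.

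Most of this stands, and it is why the point is an inconsistency of wording and not a demonstrated bias. What does not fall away is that G is mandatory, its main clause says something else, and no passage redefines that clause. G.a covers one subgroup only.

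A reader might go further and infer that the control arm was in fact built from completers, citing the reference in 9.1 to completing radiation and chemotherapy. That sentence uses the same January 2016 date as section 9 and most naturally means the same chemoradiation milestone. A reader might also infer an equal or larger bias in PFS, because 6.1.1.3.1.1 stops temozolomide at radiological progression. That rule is written for trial patients. The documents do not describe historical stopping practice, so any PFS effect cannot be sized from them.

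**Conclusion.** The inconsistency is real and should be fixed; it is not a fatal flaw. The harm is conditional on historical charts being screened on G as worded, which no passage confirms or excludes.

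Under that condition the OS comparison is biased against TTFields. Assuming 6 cycles and M=6, power is 0.84-0.86 at k=2 and 0.72-0.76 at k=1.8. At 6 cycles, across M=6 to 8, the 80% stated in 10.2 fails only at k=1.8 with M=6. The 12-cycle results (0.61-0.73 and 0.42-0.57 at M=6) are an upper bound, because they take the interventional maximum and apply it to every historical control. They should not be read as the expected loss. Nor should the point be read as a route to a false positive: type I error falls.

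The figures rest on the plan's Weibull model, the assumed cycle numbers and censoring, and a control Day 0 inferred from Table 2, 8.1.1 and the PFS definition. They count deaths only.

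**What to change.** Reword 9.2 G to: *completed chemoradiation with concurrent temozolomide and started adjuvant temozolomide (or planned, for the contemporaneous cohort)*. Add that no minimum number of adjuvant cycles is needed for eligibility. Contemporaneous controls may be enrolled while adjuvant treatment is planned, but should enter the OS analysis only once it has started.

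As a minor clarification, state that control Day 0 for OS and PFS is day 1 of adjuvant cycle 1, taken from the temozolomide dates in 9.5 item 7.

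If no site screened on completion, the cost is wording alone. Any site that did must go back for patients who started but did not finish. Counting deaths only, the number is n × q/(1 − q). At 6 cycles this runs from 60 × 0.032/0.968 ≈ 2 to 80 × 0.056/0.944 ≈ 5 charts. At 12 cycles it runs from 60 × 0.141/0.859 ≈ 10 to 80 × 0.182/0.818 ≈ 18. Section 9 says "A minimum of 90 and a maximum of 100 patients will be enrolled in the control cohort", so the cap could bind; charts should be taken consecutively within it.
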